As previously mentioned, Omegaven® may be infused in the same manner as conventional fat emulsions through either a central or peripheral line. The emulsion is isotonic. It is compatible with parenteral nutrition solutions and may be co-infused via y-site. Per Infection Control, source containers must be changed every 12 hours and unused product discarded. Omegaven® may be infused through a 1.2micron inline filter.

Dose Modification

Lipid Intolerance

If lipid intolerance develops, defined as serum triglyceride levels > 200 mg/dL, the following will be considered prior to reducing the dose:

- a) If the level was obtained while the patient was receiving a continuous 24-hour infusion of Omegaven®, the total dose should be infused over 20 hours, and a repeat serum triglyceride level obtained prior to resuming the infusion 4 hours later.

b) Other sources of lipid intolerance should be considered and addressed (drugs, renal disease)

If the triglycerides continue to remain high despite the aforementioned interventions, a dosage reduction of 25% of the current dose will be considered.

High Glucose Infusion Rate

Subjects with a high glucose infusion rate (GIR) will have a dose increase up to 1.5 grams/kg/day to allow for a reduction in PN calories from carbohydrates at the discretion of the Omegaven study team and the nutrition service.

Duration of Therapy

Patients will remain on Omegaven® until weaned from PN. Patients may continue monotherapy with Omegaven® as an additional source of calories after the dextrose/protein portion of PN is discontinued

In the event that a patient who has been listed for a liver or liver/intestinal transplant has an organ become available, the participation in this protocol will not preclude them from receiving the transplant.

Disruption of Therapy

In event that Omegaven® cannot be administered (i.e. loss of central venous catheter access, fluid restrictions, need to administer an incompatible medication/blood product), the infusion of Omegaven® may be interrupted and resumed when the conflicting situation is resolved. Some potential interventions that can be used include:

Situation	Possible Solution
Loss of central venous access	Administer via peripheral route
Fluid restriction	Consult with pharmacy to concentrate PN, medications to allow for administration

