Limited access, need to administer incompatible medications	Stop Omegaven® infusion, flush catheter with either NS or dextrose, administer incompatible medication, flush catheter, resume infusion; may be necessary to infuse Omegaven® over 8 -24 hours. Multiple syringes should be used so as to keep maximum hang time of Omegaven® source container less than 12 hours) Regardless of the infusion time, the infusion rate cannot exceed 0.15g/kg/hour.

Discontinuation of Therapy

Patients will continue to be followed by the Center for Advanced Intestinal Rehabilitation (CAIR) Program upon discontinuation of therapy with Omegaven® for a minimum of 2 months after the treatment is stopped.

Resumption of Therapy

For patients who have been off the protocol more than 1 year, in the event that the patient must receive intravenous fat emulsion, treatment with Omegaven® will resume only if the patient shows evidence of PN liver damage (elevations in direct bilirubin ≥ 2 or pathology findings consistent with cholestasis). Otherwise, the patient will be treated with conventional fat emulsion.

Soybean based Fat Emulsion (Intralipid® and/or Liposyn®)

Subjects in the Andorsky et al cohort received one of two commercially available intravenous fat emulsions (IFE), Liposyn® II or Intralipid®. IFE is provided as an oil-in-water emulsion derived from egg phospholipids, soybean or safflower oils and glycerol. Although three concentrations are commercially available (10, 20, 30%) only the 10 and 20% concentrations have been approved for use in children. Both Liposyn® II and Intralipid® contain soybean oils. Table 1 summarizes the composition of both products.

Details of IFE Administration

Regardless of the product used, doses less than 96 ml/day were repacked into syringes to allow for administration via syringe pump. Doses greater than 96ml/day were dispensed in the original manufacturer's container. If patients were discharged home on either IFE, all doses were administered from the original manufacturer's container.

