Generally, primary safety analyses will be based on time from baseline or 30 days after baseline until two months after patients first reached direct bilirubin levels $< 2\text{mg/dL}$. Baseline will be defined as information collected at the date that treatment starts for Omegaven[®] patients and on the date that patient reached bilirubin levels > 2 for soybean oil fat emulsion patients. Information on mortality and transplant will be collected during the whole treatment with Omegaven[®] and during the whole period for which we have data available in the Andorsky et al. dataset. Primary efficacy analysis will include time from baseline until the patient normalizes bilirubin (presents three consecutive direct bilirubin $\leq 2\text{ mg/dL}$ or a direct bilirubin $\leq 2\text{ mg/dL}$ and weaned from TPN). With exploratory purpose, we will also describe the curve of the several markers for the entire period that Andorsky et al. recorded data.

Outcome/Endpoints

1. Treatment safety

Our primary outcome for treatment safety will be based on patient's essential fatty acid profile. We will compare patients before treatment with Omegaven[®] started and after treatment started (one month after treatment started until treatment stopped) with respect to the frequency with which triene/tetraene ratio > 0.2 at any time. We will also compare the occurrence any event of of hypertriglyceridemia (serum triglyceride $> 400\text{mg/dL}$) between Omegaven[®] and soybean oil fat emulsions. Primary analyses for these and all other safety outcomes will be based on a follow-up time for Omegaven[®] and soybean oil fat emulsions starting 30 days after baseline, i.e., 30 days after treatment started for Omegaven[®] patients and 2 months after the first direct bilirubin level $< 2\text{ mg/dL}$ was recorded. We will also explore comparisons including the time from baseline until the end of follow-up period.

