Additional comparisons across treatment periods for subjects receiving Omegaven® will be aimed to assess occurrence of spontaneous bleeding (e.g., unexplained bruising, oozing from gums/incision sites), and maximum triene/tetraene ratio, minimum platelets, and maximum international normalized ratio (INR), trends in pre-albumin (age standardized levels). We will also explore trends in coagulopathies based on curves of platelets, prothrombin time (PT), partial thromboplastin time (PTT) over time, and INR. We will also describe the rate with which INR ratios were > 2 (number of days/follow-up time), as a marker of coagulopathies.

Additional comparisons between Omegaven® and soybean oil fat emulsion groups will be performed with regards to rate in which albumin is > 3 g/dL, maximum triglyceride level, rate of blood stream infections (number of positive blood cultures/follow-up-time under PN after baseline), rate of central venous catheter (CVC) infections (number of CVC infections/follow-up time and number of gram positive CVC infections/follow-up time), and occurrence of anaphylactic reactions after baseline.

Nutritional outcomes between Omegaven® and soybean oil fat emulsion groups that will be compared include changes in weight- and height-for-age Z-scores from baseline to 10% PN or cessation of PN..

We will describe trends over time for all outcomes associated with fatty acid profiles (including triene/tetraene ratios, triglycerides, total omega-6 fatty acids, total omega-3 fatty acids, total saturated, total monounsaturated, and total polysaturated fatty acids). Specific fatty acids such as arachidonic, palmoleic, palmitic, oleic, stearic, and linoleic fatty acids will also be evaluated and described. Also, for exploratory purposes, we will compare the trend in weight- and height-for-age Z-scores between both groups.

2. Omegaven®

3. The patient will complete treatment with Omegaven® in this study when he/she is completely off PN, develops a contraindication for further use, or the patient/family requests to be removed from the study.

f. Data Collection Methods, Assessments and Schedule

Omega-3 Fat Emulsion (Omegaven™)

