Adverse events (AEs) will be assessed and reported from the time of the first Omegaven® infusion until exit from the study in accordance with CHB Committee on Clinical Investigations (CCI) reporting requirements. In particular, the patient will be observed during and shortly after Omegaven® administration for the occurrence of anaphylactic or allergic reactions. Other expected adverse events include death, blood stream infection; transfer to ICU for treatment of respiratory distress or hemodynamic instability; re-hospitalization for treatment of blood stream infection, dehydration, electrolyte abnormalities, catheter malfunctions, bowel obstructions, and urinary tract infection. Unexpected adverse events will also be assessed and reported in compliance with the CHB CCI requirements. Patients experiencing any adverse events that are moderate or severe in nature and that may be related to Omegaven® will have their treatment temporarily halted until the adverse event has resolved. Dose modifications will occur as described above. If a dose reduction is made for adverse events later considered to be unrelated to Omegaven®, the Omegaven® dose will be increased back to the dose prescribed prior to the dose reduction. Patients with anaphylactic or allergic reactions will not continue Omegaven® treatment.

Any serious or unsuspected adverse events will be reported to the Committee on Clinical Investigation (CCI) and the FDA within 72 hours of the occurrence of being known, or immediately if the event is fatal or life threatening as per Children's Hospital Policy on Adverse and Unexpected Events and Unanticipated Risks to Research Subjects and Others. This will be done in person, by telephone, or email, and by completion of the CCI's form for adverse/unexpected event reporting.

Adverse events are detected by CHB acute care medical and nursing staff during provision of standard care services including the routine monitoring of vital signs and daily physical exam data. Adverse events identified by CHB staff are reported to the Principal Investigator immediately by telephone or pager, and subsequently to the appropriate board or committee.

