A Committee of the Study Investigators (Drs. [name], [name], and [name]) will be responsible for assuring that adverse event reporting requirements are actually met. The Investigator Committee will meet not less than monthly to conduct clinical case reviews of all patients receiving Omegaven® to review recruitment data, adverse events and protocol deviations; and to evaluate overall safety of Omegaven® therapy. CHB Staff dieticians caring for Omegaven® patients will participate in the Investigator meetings as necessary. Any patients who have agreed to participate in the trial, but who have not yet undergone intervention, will be informed of adverse events. A revised consent document will be submitted to the CCI with the adverse event form for review and approval. All adverse events will be classified by the Principal Investigator as definitely, probably, possibly, or unrelated to administration of study drug.

Patients will be withdrawn from the study for any of the following:

- a) Toxicity considered unacceptable by the Principal Investigator
- b) Patient/guardian requests to discontinue treatment and/or observation for any reason.
- c) A suitable organ has been located and the patient is able to undergo a liver or liver/intestinal transplant.
- d) Decision by the Principal Investigator that termination is in the patient's best medical interest.
- e) Patient is lost to follow up.

In the event that a patient is withdrawn from the protocol, study staff will document the date of withdrawal, the reason for withdrawal, and the results of all measurements of interest made up to date of withdrawal.

5. Data Management and Statistical Analysis

a. Data Management Methods

Overview

All clinical and laboratory research data will be abstracted from source documents (medical records) and recorded and maintained on study specific case report forms (CRF). These CRFs will be stored within individual subject binders in accordance with Good Clinical Practice Standards and FDA requirements. Study materials will be kept in the Principal Investigator's locked office and access will be restricted to authorized study staff only. Subject confidentiality will be maintained by recording subject-specific data using a unique confidential study identifier.

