We will also describe individual profiles over time (i.e., 2 months before baseline or birth until end of follow-up period) for all subjects using graphical methods. Trends in liver function markers over time will be explored using generalized linear models in which correlations of observations within subjects will be accounted using a generalized equations or random effects approach. In these models we will hypothesize that for both groups biochemical levels increase for all tests with equal slope before treatment. After treatment, however, levels should be decreasing for patients in the Omegaven® group. We will perform these analyses including only subjects who did not die or undergo transplantation and including all subjects but assigning for subjects who died or underwent a transplant their worse possible outcome after they died or had the transplant. Using descriptive statistics, we will also explore the association between spikes in blood tests over time and predictors including transfusions of red blood cell products and blood stream infections.

Assessment of efficacy will be also based on comparison of means (or medians) of the mean and maximum modified PELD scores of each subject across all follow-up weeks. Adjustments of these comparisons for potential confounders will be based on linear regression models. Mean rates of infection will be compared using logrank and Cox proportional hazards models. Proportions of liver transplant, mortality, and red blood cell product transfusion events between the two groups will be compared via Fisher's exact test (or Chi-square tests, when appropriate). Adjustments for potential confounders will be considered using exact stratified analysis and logistic regression models.

Missing Values

Since data will be prospectively collected in the Omegaven® group, we anticipate that data will be nearly complete, particularly for the safety outcomes. In both groups, we will explore imputing any laboratory values that are missing up to two visits in the middle of the follow-up period using linear or non-linear interpolation, as appropriate. To interpolate direct and total bilirubin, we will primarily use the two closest observations, since bilirubin could be very different in points in time located further apart from the missing observation. We will compare conclusions of analyses based on imputed values with analyses based on the available information.

Potential Study Limitations

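### Death and transplant are collected over different windows in the two groups and compared as crude proportions, with no statement of which window applies and no time at risk

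*Combined protocol and SAP*

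**What the plan says.** All references are to the combined protocol and SAP.

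- **Collection window** (section e, Definition of Primary and Secondary Outcomes/Endpoints): "Information on mortality and transplant will be collected during the whole treatment with Omegaven[®] and during the whole period for which we have data", the data being those of the original historical control study.
- **End of Omegaven treatment** (section d, Duration of Therapy): "Patients will remain on Omegaven® until weaned from PN". Section e agrees: "The patient will complete treatment with Omegaven® in this study when he/she is completely off PN", or earlier for a contraindication or at the family's request.
- **After treatment** (section d, Discontinuation of Therapy): Omegaven patients are followed "for a minimum of 2 months after the treatment is stopped".
- **Adverse events** (section h): these, with death on the list, "will be assessed and reported from the time of the first Omegaven® infusion until exit from the study".
- **Withdrawal** (section h): one reason is "A suitable organ has been located and the patient is able to undergo a liver or liver/intestinal transplant". Another is a guardian's request to stop treatment, observation or both. Measurements are kept up to the withdrawal date.
- **Control follow-up** (design paragraph before section b): primary follow-up of the original controls stops 2 months after bilirubin normalisation, death or transplant. Use of their entire follow-up is called exploratory.
- **Analysis** (section 5c, Analysis of Efficacy): "Proportions of liver transplant, mortality, and red blood cell product transfusion events between the two groups will be compared via" Fisher's exact or chi-square tests, with stratified exact analysis or logistic regression for adjustment. The same paragraph says "Mean rates of infection will be compared using logrank and Cox proportional hazards models".

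The visible text gives no death or transplant window for the second control cohort (1999-2004).

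**The concern.** Hypothesis 2.4 expects fewer transplants and hepatic deaths with Omegaven. A proportion of patients with an event grows with the time over which they are watched. If one group is watched while on treatment and the other for as long as records exist, the proportions can differ even when the underlying risks are the same. Fisher's test, chi-square and logistic regression on event status have no term for this.

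The Omegaven window also closes at a point linked to recovery. Coming off PN is itself a good sign, so a later death or transplant falls outside the section e wording for an Omegaven patient but inside it for an original control. At stake is the estimate for a secondary comparison of the two most serious outcomes. The primary bilirubin endpoint is not at stake: section 5c handles death and transplant there explicitly, by assigning an infinite time to normalisation.

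**Working it through.** **1. The plan's own figures for this test.** Table 5 gives the power of Fisher's exact test for adverse events with 20, 25 or 30 per group. Full enumeration of two binomials, two-sided at 0.05, reproduces all 18 cells within 0.5 points. For example, a difference of 35% from 5% at n = 20 is stated as 72% and computed as 71.6%; 45% from 25% at n = 20 is stated as 73% and computed as 73.1%. Nothing comparable is given for death or transplant.

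**2. Which windows could feed the test.** For the original controls, the section e window and the design-paragraph window differ in two ways: events more than 2 months after normalisation, and deaths more than 2 months after transplant. For Omegaven patients the window is treatment, possibly plus the minimum 2 months. A transplant that triggers withdrawal is recorded as the reason for withdrawal. No visible passage says how a death after transplant, or an event after withdrawal for another reason, is captured.

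**3. How much unequal windows could matter.** The documents give no hazards, PN durations or window lengths, so every input here is assumed. Let the event hazard be h = 1% per month on PN in both groups, PN end at month 6, and the hazard after PN be r times h. Then

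risk to month T = 1 - exp(-h × min(T, 6) - r × h × max(0, T - 6)).

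For 8 versus 12 months with r = 1, the risks are 1 - exp(-0.08) = 7.7% and 1 - exp(-0.12) = 11.3%, so the odds ratio is (0.0769/0.9231)/(0.1131/0.8869) = 0.65. For 8 versus 24 months the control risk is 1 - exp(-0.24) = 21.3%, and the odds ratio is 0.31.

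Odds ratios (Omegaven versus control) when there is no true difference in hazard:

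| Omegaven / control window (months) | r = 1 | r = 0.5 | r = 0.25 | r = 0 |
|---|---|---|---|---|
| 8 / 9 | 0.88 | 0.93 | 0.96 | 1.00 |
| 8 / 12 | 0.65 | 0.77 | 0.86 | 1.00 |
| 6 / 12 | 0.49 | 0.66 | 0.79 | 1.00 |
| 8 / 24 | 0.31 | 0.45 | 0.61 | 1.00 |
| 6 / 24 | 0.23 | 0.38 | 0.56 | 1.00 |
| 12 / 6 (reversed) | 2.06 | 1.52 | 1.26 | 1.00 |

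The 8-month rows credit the 2 months of follow-up after treatment. The level of the hazard matters little to the odds ratio: for 8 versus 12 months at r = 1 it is 0.66 at 0.5% per month and 0.64 at 2%.

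**4. False rejection.** For 8 versus 24 months at h = 1% per month, Fisher's test rejects in at most 18.4%, 4.7% and 1.4% of studies (r = 1, 0.5, 0.25) with 20 to 30 per group. With 50 per group and r = 1 it rejects in 37.9%. For 8 versus 12 months with 20 to 30 per group the maxima are 1.7%, 0.8% and 0.5%.

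**5. With a common horizon.** At 12 or 24 months for both groups, h = 1% per month and r = 1, 0.5 or 0.25, Fisher's test rejects in 0.3% to 2.9% (n = 20 to 50 per group). The log-rank test rejects in 4.4% to 5.9% (4,000 simulations per setting, n = 30 and 50 per group).

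**The case against.** The strongest reply is that section e describes what is collected, not what is analysed. Read with the design paragraph, control follow-up could be cut at 2 months after normalisation or transplant; Omegaven patients are followed for at least 2 months after treatment, and deaths are reported until study exit. On that reading the plan is underspecified and no mismatch has been shown. This stands in part. It is why the point is that the passages must be reconciled, and why a reader who infers a proven mismatch goes too far. It does not remove the point: none of those provisions is tied to the comparison, and section 5c does not choose between the readings.

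A second reply is that the answer may sit in text not available here. The efficacy list in section e appears to be cut, and text before the design paragraph was not seen. That is a fair limit on every statement that a window is absent, above all for the 1999-2004 controls.

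Third, the illustration ends PN at month 6 for everyone, whereas patients who are not weaned stay on Omegaven and inside their window. That also stands, and the table should not be read as a prediction.

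Finally, the comparison is secondary, group sizes were not set by power, and the limitations section already names poor comparability. That limits the weight of the point. The limitations section does not, however, mention unequal observation time.

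**Conclusion.** The concern holds in a limited form. As written, the plan allows the death and transplant comparison to reflect length of observation as well as risk, and it does not say which control window applies. The shift in the odds ratio ranges from none to large, depending wholly on assumed window lengths and on the risk after PN.

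Three stronger inferences are not supported:

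- **That the bias favours Omegaven.** It does so only if the control window is the longer; the visible text gives no lengths.
- **That the false-positive rate is high.** Equal hazards of 0.4 per year with windows of 6 months versus 3 years give 98.1% at 30 per group, but that is a product of the chosen inputs.
- **That the false-positive rate is low.** The small figures depend on 20 to 30 per group. Omegaven enrolment is not fixed by power, and the second control cohort is planned at 50.

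No general statement about the false-positive rate should be made. This should be fixed, because the outcomes are serious and the repair is modest. Confidence is medium, since the size cannot be estimated from the documents.

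**What to change.** 1. Reconcile the design paragraph, section e and section 5c, and state which window feeds the death and transplant comparison.
2. Count both outcomes from baseline to one common horizon in all groups, including the 1999-2004 controls. Choose it on completeness of records, not on outcomes. The section on contemporary controls refers to prior comparative analyses; if outcomes have already been compared, say so. Do not end the analysis window at PN weaning.
3. Use existing records to establish vital and transplant status to that horizon in all groups, including deaths after transplant. Leave out families who have withdrawn from observation, and censor those patients at withdrawal.
4. Analyse by log-rank and Cox methods with censoring, and show cumulative incidence of transplant with death as a competing event. Keep Fisher's test only if status is complete to the horizon.
5. State that baseline still differs by group (start of treatment for Omegaven, first bilirubin above 2 mg/dL for controls). A common horizon does not remove that difference.

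The cost is a protocol and SAP amendment with IRB approval, as the section on legal and ethics requirements demands, and a limited record review, partly at other facilities. Control events after the horizon leave the main comparison and become exploratory, as the design paragraph already provides.
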